8. ADVERSE EVENT REPORTING

Throughout the study, AEs will be recorded in the source documents and transcribed onto the appropriate pages of the eCRF regardless of whether the AEs are considered treatment related. All AEs with onset dates from signature of the ICF through study exit will be recorded as an AE on the eCRF. All SAEs with onset dates from signature of the ICF through study exit must be recorded following the guidelines in Sections 8.4, 8.6, 8.7, 8.8 and 8.9. Any AE that occurs at any time after completion of the study, which the investigator considers to be related to study drug, must be reported.

Conditions existing prior to screening will be recorded as part of the patient's medical history. To avoid confusion, the AE should be recorded in standard medical terminology. The Investigator is responsible for assessing the relationship of AEs to the AG019 as well as to teplizumab (Section 8.3).

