3 EFFICACY AND SAFETY ENDPOINTS

3.1 Primary Endpoint

The primary endpoint will be assessed by analysis of the incidence of treatment-emergent adverse events (TEAEs) collected up to the 6-month follow-up visit. A TEAE is defined as any adverse event (AE) not present prior to the initiation of the treatment(s) or any AE already present that worsens in either intensity or frequency following exposure to the treatment(s).

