6.3.7 Concomitant Medications

All concomitant medications/therapies (including insulin medication) will be classified according to ATC level 3 group text and World Health Organization (WHO) Drug Dictionary preferred name. The medications will be divided into two timing categories based on start date and end date: Prior and Concomitant Medications:

- Prior Medications: start date and end date before first day of IMP
- Concomitant Medications:
 - o Start date before first day of IMP and end date after or on same day as first day of IMP or no end date, i.e. ongoing after first day of IMP; or
 - o Start date after or on same day as first day of IMP

If the date for a concomitant medication is completely missing, it will be assumed that the medication was started before treatment and classified as Prior Medication. If the year and/or month are available, medication start in relation to the first day of IMP will be evaluated as far as possible (e.g., if only the year when the medication was started is available and ongoing is checked, the medication will be classified as a Concomitant Medication). If the medication was started in the same month as the first day of IMP, the medication will be classified as a

Concomitant Medication. Relative day will not be calculated for medications with incomplete dates.

The concomitant medications will be presented in a summary table according to timing in relation to IMP (i.e., Prior and Concomitant). Each subject will only be counted once for each medication and timing category, on a preferred name level.

One list for each timing category (Prior and Concomitant) will be presented.

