6.3.8 Adverse Events

AEs will be coded according to the Medical Dictionary for Regulatory Activities (MedDRA) system.

The severity of adverse events will be given in grades 1 to 5 per National Cancer Institute common terminology criteria for adverse events (CTCAE) version 4.0.

All AEs were categorized by the Investigator with respect to their possible relationship to the IMP. The relationship of the AE to AG019, as well as the relationship of the AE to teplizumab, will be assessed separately by the investigator to be not related, unlikely, possible, probable or definite. The categorization:

- reasonably related defined as possible, probable or definite versus
- not reasonably related defined as not related or unlikely will be given in summaries of all adverse events.

If a subject has more than one event with the same preferred term (PT), then the worst severity and the worst relationship will be used.

A TEAE is defined as any adverse event (AE) not present prior to the initiation of the treatment(s) or any AE already present that worsens in either intensity or frequency following exposure to the treatment(s). Hence, events with an onset time at or after the time of treatment start are treatment emergent. Events present at baseline that worsen during the study in either intensity or frequency are also treatment emergent, whereas events present at baseline that become less severe during the study are not. Events that recur during the study are treatment emergent if they recur after complete or partial recovery of the initial event, i.e. should the event first become less severe and then return to its initial severity, it will be considered as a TEAE. AEs reported on the same day as treatment start or after treatment start will be considered TEAEs, as investigators are instructed only to report TEAEs after treatment start.

A Serious Adverse Event (SAE) is defined as any AE occurring at any dose regardless of relationship to IMP that results in any of the following outcomes:

- results in death,
- is life-threatening,
- requires inpatient hospitalisation or prolongation of existing hospitalisation,
- results in persistent or significant disability/incapacity, or
- is a congenital anomaly/birth defect.

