If the start date of an AE is missing, it will be assumed that the AE started after the first administration of IMP. If the start date of an AE is partially missing, and it has started the same year and/or month as the IMP it will be assumed that the AE started after the first administration of IMP. If an AE occurred on the same day as dosing but the onset time is missing the AE will be assumed to be a TEAE.

The infusion of teplizumab was considered withheld if the answer to the CRF question 'Was the Teplizumab infusion given?' was 'No, infusion not started' and/or if the answer on the AE page on 'Action Taken With Study Treatment Teplizumab' was 'Drug interrupted' or 'Drug withdrawn'.

Study treatment of AG019 was considered discontinued if the answer to the CRF question "Action Taken with Study Treatment AG019" was "Drug interrupted" or "Drug withdrawn".

A summary table per cohort will present number of TEAEs, number of unique TEAEs (counted once within each subject at the preferred term level) and number of subjects with at least one event for TEAEs, SAEs, related TEAEs, TEAEs leading to discontinuation of IMP/withdrawal and more.

Tables with

- All AEs by System Organ Class (SOC) and PT,
- All TEAEs by SOC and PT, in total and for the AG019 treatment period only,
- All TEAEs by SOC and PT according to severity, in total and for the AG019 treatment period only,
- All TEAEs by SOC and PT according to relatedness, in total and for the AG019 treatment period only,
- All serious TEAEs by SOC and PT,

will be given. If there are no events an empty table will be produced.

All AEs will be listed. In addition all TEAEs leading to AG019 treatment discontinuation and study infusion withholding will be listed.

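### The SAP's rule for partial and missing AE start dates can be read to count events known to be pre-dose in the primary TEAE endpoint, and needs one clarifying sentence

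*SAP*

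**What the plan says.** The primary endpoint is the "incidence of treatment-emergent adverse events (TEAEs) collected up to the 6-month follow-up visit" (SAP 3.1). SAP 6.3.8 operationalises this by onset: "events with an onset time at or after the time of treatment start are treatment emergent". An event already present counts if it worsens after exposure.

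Two rules in SAP 6.3.8 deal with incomplete onset dates:

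- Fully missing: "If the start date of an AE is missing, it will be assumed that the AE started after the first administration of IMP".
- Partly missing: where "it has started the same year and/or month as the IMP it will be assumed that the AE started after" first dosing.

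SAP 6.6 refers back to this section and adds no other AE date rule. The parallel rule for medications (SAP 6.3.7) is worded differently. When the year or month is available, "medication start in relation to the first day of IMP will be evaluated as far as possible", and the end date helps to decide whether a medication is prior or concomitant.

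Pre-dose AEs are in the database by design. Protocol Section 8 states: "All AEs with onset dates from signature of the ICF through study exit will be recorded as an AE on the eCRF". Screening may run for up to 28 days before the first dose (Protocol Section 4).

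**The concern.** Assuming post-dose onset is sound when the timing is unknown. The difficulty arises when the recorded parts of the date already settle it. Take an AE recorded as July 2020, day unknown, in a patient first dosed on 12 August 2020. Every day in July precedes the dose, yet the year matches, and with an *or* in the rule a year match is sufficient. The event would be flagged as treatment-emergent with no worsening on treatment, contrary to the SAP's own TEAE definition.

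Likewise, an AE with no start date but a stop date before first dosing cannot have begun after it, yet the rule for missing dates still assumes that it did.

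The flag defines the primary endpoint and feeds the TEAE tables by severity and relatedness. Groups are very small, so a single event can show in a reported percentage.

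**Working it through.** The plan states no figure to reproduce. The check has three parts.

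**1. Apply the rule to worked cases**

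| Recorded onset | First dose | Literal rule (year or month matches) | Comparing year and month together |
|---|---|---|---|
| July 2020, day unknown | 12 Aug 2020 | TEAE (year matches) | Not a TEAE on onset |
| May 2019, day unknown | 10 Jun 2019 | TEAE (year matches) | Not a TEAE on onset |
| Dec 2018, day unknown | 5 Jan 2019 | Not assumed post-dose (no match) | Not a TEAE on onset |

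The two readings therefore differ only within one calendar year.

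**2. Share of pre-dose AEs with unknown day that the literal rule misclassifies**

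Inputs:
- The window W is the number of days before first dose over which onset can fall. Its maximum is 28 (Protocol Section 4). I use 7, 14, 21 and 28.
- Assumptions not in the documents: the first-dose date is uniform over a 365-day year, and onset is uniform over days 1 to W before it.

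If the first dose is on day d of a month (d = 1 to W), lags of d to W days put onset in the previous month. That is W − d + 1 lags, which sum to W(W+1)/2 per month. Every month has at least 28 days, so this is exact for W up to 28. January dosing puts onset in December of the previous year, which matches neither year nor month, so 11 of the 12 month boundaries count. There are 365 × W date-lag pairs in all.

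Misclassified share = 11 × W(W+1)/2 ÷ (365 × W) = 11(W+1)/730

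TEAE share, literal rule = 1 − (W+1)/730

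TEAE share, year and month compared together = 1 − 12(W+1)/730

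| W (days) | Literal rule | Year and month together | Misclassified |
|---|---|---|---|
| 7 | 98.9% | 86.8% | 88/730 = 12.1% |
| 14 | 97.9% | 75.3% | 165/730 = 22.6% |
| 21 | 97.0% | 63.8% | 242/730 = 33.2% |
| 28 | 96.0% | 52.3% | 319/730 = 43.7% |

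Direct enumeration of all date-lag pairs gives the same results. The share still called TEAE in the third column is the case of same year and month with unknown day. That is ordinary conservative practice and is not at issue.

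**3. Effect of one misclassified AE on incidence**

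Repeat-dose AG019 cohorts have 4 to 6 patients (SAP 4.1.1). If the affected patient has no other TEAE, incidence moves by 1/6 = 17 points to 1/4 = 25 points. In each combination cohort, 10 patients are randomised 4:1, so 2 receive placebo, and the same event there would move that group by 1/2 = 50 points.

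The stop-date gap needs no arithmetic: the SAP 6.3.8 imputation rules do not refer to the stop date.

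**The case against.** The strongest reply is that the wording need not bear the literal meaning. Year and/or month can mean whichever parts are recorded: compare the year if only the year is known, and both if both are known. SAP 6.3.7 uses the same phrase in that sense. The literal *or* would also match an AE in August of one year to dosing in August of another, which no author would intend. The TEAE definition itself requires an event not present before treatment. This stands as far as intent goes. It does not settle the text, because no sentence limits the year match to cases where the month is unknown. Nor does it touch the stop-date gap.

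The second reply concerns size. The percentages apply to a count that the documents do not give: AEs with onset between consent and first dose and with the day missing. Repeat-dose patients keep an electronic diary from consent, reviewed at every follow-up visit (Protocol 6.4.1), and questionable data are queried (Protocol 12.3). Such AEs should be rare. The 17 to 25 point shift also needs a patient with no other TEAE over six months. Both limits stand.

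The third reply is that over-counting is conservative in a descriptive study without tests, that all AEs are listed with their dates, and that a blind review is planned (SAP 6.2). This mostly stands. One reservation is that over-counting in a two-patient placebo group raises the comparator rate and so narrows the visible contrast with active treatment.

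SAP 6.3.8 also says that investigators are instructed to report only TEAEs once treatment has started. That does not help with AEs already recorded during screening.

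**Conclusion.** The point holds as an ambiguity with a real consequence. Read literally, the rule sends AEs known to be pre-dose into the primary endpoint, and nothing in the SAP excludes that reading. The rule for missing dates ignores a stop date that would settle the matter.

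Under the literal reading, about 12% to 44% of pre-dose AEs with unknown day are misclassified as the window runs from 7 to 28 days. This rests on uniform dosing and onset dates. The upper figure requires onsets spread over the full 28-day maximum.

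A reader might infer more than this, and the documents do not support it:

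- That the SAP demonstrably overrides known dates. The alternative reading is plausible, and even the literal rule does not pull in a December onset before January dosing.
- That 44% of screening AEs, or of TEAEs, are wrong. The figure is the top of a range, and its base is an unstated and probably small number of events.
- That incidence will be off by 17 to 25 points. That is the effect of one such event in a patient with no other TEAE, not an expected bias.
- That assuming post-dose onset is itself a fault. It is reasonable when neither the known date parts nor the stop date show otherwise.

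No test or sample-size conclusion is affected. The point still merits correction, because the flag defines the primary endpoint and the remedy is trivial.

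**What to change.** Replace the two date sentences in SAP 6.3.8 with:

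> For an AE with a missing or partial start date, onset is assumed to be on or after first IMP unless the known date parts (year, or year and month together) or a known stop date show that it was before first IMP. Same year and month with unknown day is assumed to be on or after first IMP. This governs imputed onset only: AEs with pre-dose onset that worsen in intensity or frequency after first IMP remain TEAEs.

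The last sentence is needed. A rule saying that an AE is not a TEAE whenever onset is shown to be pre-dose would drop pre-existing events that worsen on treatment, which SAP 3.1 and 6.3.8 count. That would under-count harm.

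The cost is this short SAP edit and one derivation line, with no change to data collection. It should be settled before the third interim unblinding, when SAP 6.9 says that decisions on blinded subjects' data will already have been taken.

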5. STUDY TREATMENT

5.1.Treatments

5.1.1AG019

Single dose patients will be treated with (2 or 6 capsules of) AG019.

All patients in the repeat dose cohorts, and all patients in the combination cohorts who are randomized to study treatment, will be treated for 8 weeks with AG019 with one of the doses listed in Table 2:

Table 2: AG019 dosing regimens for repeat dose patients

Dose	Number of capsules	Total daily dose	Treatment duration
Low dose AG019	2 (1 morning, 1 evening)	XXX	8 weeks
High dose AG019	6 (3 morning, 3 evening)	xxx	8 weeks

The total treatment duration for repeat dose patients is 8 weeks or 56 days. Patients will be required to take AG019 for 56 days, even if the Day 56 follow-up visit is not scheduled on Day 56 (there is a 2-day visit window on the Day 56 follow-up visit).

- If the Day 56 follow-up visit is scheduled on Day 54 or Day 55, patients will take their remaining AG019 home again and will continue to take AG019 until the evening dose on Day 56. The patients will then take their remaining AG019 back to the site on Day 90 for final accountability
- If the Day 56 follow-up visit is scheduled on Day 57 or Day 58, patients should be instructed to take AG019 until the evening dose on Day 56.

The daily dose of AG019 to be used in the Phase 2a portion of the study (combination cohorts) is not yet known and will be determined by the results of the Phase 1b portion of the study (AG019 cohorts). Based upon the data obtained in the nonclinical studies, the Sponsor anticipates that a 6-capsule regimen will be administered in the combination cohorts. Following rules will apply:

If the DSMB concludes that no safety concerns are associated with the high dose of AG019 (6 capsules per day) in the Phase 1b portion of the study (AG019 cohorts), the patients enrolled

Confidentiality Statement

in the Phase 2a portion of the study (combination cohorts) will take the high dose of AG019 for 8 weeks.

If the DSMB concludes that safety concerns are associated with the high dose of AG019 (6 capsules per day) in the Phase 1b portion of the study (AG019 cohorts) and that no safety concerns are associated with the low dose of AG019 (2 capsules per day), the DSMB will recommend lowering the AG019 dose in all ongoing and planned (AG019 and) combination cohorts.

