4.1.1 Phase 1b

This open-label part of the study will investigate the safety and tolerability of different doses of AG019, in 2 age groups (18-42 years of age and 12-17 years of age, respectively), administered as single or repeat doses. Patients were enrolled in 4 sequential cohorts (AG019 cohorts):

- **AG019 Cohort 1:** 2 capsules per day, patients 18-42 years
- **AG019 Cohort 2:** 6 capsules per day, patients 18-42 years
- **AG019 Cohort 3:** 2 capsules per day, patients 12-17 years
- **AG019 Cohort 4:** 6 capsules per day, patients 12-17 years

Single dose patients

In every AG019 cohort, 2 single dose patients were enrolled in a first stage. Each of these patients were treated for 1 day with AG019 (2 or 6 capsules of XXX Colony Forming Units [CFU], depending on the cohort), and were followed up for a total of 4 days (treatment day [Day 1] plus 3 additional days), after which they had completed their study participation (Day 4).

Repeat dose patients

A minimum of 4 repeat dose patients were enrolled per AG019 cohort. In addition, both single dose patients in each AG019 cohort were offered the option of being re-enrolled as repeat dose patients in the same AG19 cohort. Therefore, if both single dose patients agree to be re-enrolled as repeat dose patients, the maximum number of repeat dose patients per cohort were 6. All repeat dose patients were planned to be treated for 8 weeks with AG019 and followed up for a total of 12 months (8 weeks of treatment plus 10 months of post-treatment follow-up).

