14.3 SAFETY DATA

(Safety presentations will be based on the safety set unless otherwise stated below)

- 14.3.1.x Summary of All Adverse Events for single dose AG019 patients
- 14.3.1.x Summary of All Adverse Events for repeat dose AG019 patients
- 14.3.1.x Summary of All Adverse Events for combination cohort patients
- 14.3.1.x All Adverse Events by System Organ Class and Preferred Term
- 14.3.1.x Treatment-Emergent Adverse Events by System Organ Class and Preferred Term
- 14.3.1.x Treatment-Emergent Adverse Events by System Organ Class and Preferred Term during AG019 treatment period
- 14.3.1.x Treatment-Emergent Adverse Events by Severity, System Organ Class and Preferred Term
- 14.3.1.x Treatment-Emergent Adverse Events by Severity, System Organ Class and Preferred Term during AG019 treatment period
- 14.3.1.x Treatment-Emergent Adverse Events by Relationship to AG019, System Organ Class and Preferred Term
- 14.3.1.x Treatment-Emergent Adverse Events by Relationship to AG019, System Organ Class and Preferred Term during AG019 treatment period

14.3.1.x Treatment-Emergent Serious Adverse Events by System Organ Class and Preferred Term

14.3.1.x Treatment-Emergent Adverse Events Leading to Premature AG019 Treatment Discontinuation by System Organ Class and Preferred Term

14.3.4.x Laboratory Measurements:
Summary Statistics by Visit with Difference from Baseline (Hematology & INR, Clinical Chemistry, Liver Function & CRP and HbA1c)
Shift Tables (Hematology & INR, Clinical Chemistry, Liver Function & CRP)
Figures of mean and median CRP, AST and Lymphocytes over time
Number of patients with positive/negative serology at baseline and positive/negative for PCR per visit
Summary of CGM Recording Time

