14.3.5 Compliance to treatment with AG019
Compliance to treatment with teplizumab

14.3.6.x Vital Signs:
Summary Statistics with Difference from Baseline
Shift Tables

14.3.7.x Physical Examination per visit and treatment

14.3.8.x ECG per visit and treatment

14.3.9.x Summary of Hypoglycemic Events

14.3.10.x Concomitant Medication and Therapy (including insulin medication)
• Prior Medications and Therapies
• Concomitant Medications and Therapies

7.2 Listings of Individual Patient Data and Other Information to be Produced for the Clinical Study Report (Sections 16.1 and 16.2 in ICH E3)

(Listing numbers refer to the relevant appendix number in ICH E3. CRF check questions/reminders will not be listed.)

16.2.1.x Discontinued Patients, Reason for Discontinuation
Visit Dates and AG019 Treatment End Date

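### AG019 interruptions are counted as premature discontinuation, and no planned relatedness table covers teplizumab

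*SAP*

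**What the plan says.** **Discontinuation.** SAP 6.3.8 states that AG019 study treatment is "considered discontinued if the answer to the CRF question 'Action Taken with Study Treatment AG019' was 'Drug interrupted' or 'Drug withdrawn". The same section plans a listing of treatment-emergent events that led to AG019 discontinuation. The output list in SAP 7.1 (14.3 Safety Data) plans a table of "Treatment-Emergent Adverse Events Leading to Premature AG019 Treatment Discontinuation by System Organ Class and Preferred Term". For a completed course, Protocol 5.1.1 says "Patients will be required to take AG019 for 56 days".

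**Relatedness.** Protocol sections 8 and 8.3 and SAP 6.3.8 have the investigator rate each event twice, once against AG019 and once against teplizumab. SAP 6.3.8 then plans "All TEAEs by SOC and PT according to relatedness, in total and for the AG019 treatment period only", without limiting relatedness to one product. SAP 7.1 lists two such tables: one by relationship to AG019 overall, and "Treatment-Emergent Adverse Events by Relationship to AG019, System Organ Class and Preferred Term during AG019 treatment period". Protocol 10.7 commits to separate summaries of treatment-emergent events related to either investigational product. SAP 6.1 reports no changes to the planned analyses.

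**The concern.** The primary objective is safety and tolerability, of AG019 alone and in association with teplizumab. How often patients stopped AG019 because of an event, and which product an event was attributed to, are two tolerability results that readers will look for.

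A table titled premature discontinuation that also holds resumed pauses overstates the number of stops. Protocol 10.2 says the study is to inform the design of later studies, and an inflated discontinuation count is a poor input to that.

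On attribution, Protocol 8.10 expects no adverse events from AG019 apart from possible sepsis, and for teplizumab it introduces the most common drug-related events. Teplizumab is therefore the product with a known event profile, yet no relatedness table by system organ class and preferred term is planned for it.

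**Working it through.** The plan states no figure on this point, so the check compares passages and then uses simple counts.

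**Discontinuation**

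1. Rule (SAP 6.3.8): a CRF action of either *interrupted* or *withdrawn* makes AG019 discontinued.
2. Output (SAP 7.1): one table, whose title refers to premature AG019 discontinuation. With no other definition in the SAP, the rule in step 1 populates it.
3. Test case: a patient pauses capsules for an event, resumes, and takes the last dose on Day 56. Step 1 puts that patient in the table. The SAP 7.2 listing "Visit Dates and AG019 Treatment End Date" would show a completed course. The two outputs disagree about the same patient.
4. For teplizumab, SAP 6.3.8 labels the same two CRF answers as an infusion withheld. Identical answers therefore carry different labels for the two products.
5. No planned table separates the two answers for AG019.

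**Relatedness**

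| Source | What it provides |
|---|---|
| Protocol 8.3, SAP 6.3.8 | Two ratings per event: AG019 and teplizumab |
| Protocol 10.7 | Summaries of events related to either product |
| SAP 6.3.8 | Relatedness tables, product not named |
| SAP 7.1 | 2 tables by AG019, 0 by teplizumab, 0 by either product |
| SAP 6.1 | No change declared |

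An event rated related to teplizumab but not to AG019 falls under not related in both listed tables.

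**Size**

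- AG019 repeat-dose cohort: SAP 4.1.1 says "A minimum of 4 repeat dose patients were enrolled per AG019 cohort", with a maximum of 6. One resumed pause is 1/4 = 25% or 1/6 = 16.7%.
- Combination cohort (SAP 4.1.2): 2 open-label patients plus 10 randomized 4:1. Active = 2 + 10 × 4/5 = 10; placebo = 10 × 1/5 = 2. One resumed pause on active treatment is 1/10 = 10%.
- Planned teplizumab recipients: 2 × 10 = 20 of 24; the other 2 × 2 = 4 receive placebo.

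The percentages show what one such patient would add. They do not estimate how often it will happen.

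**The case against.** **On discontinuation.** The rule is explicit and any programmer would apply it the same way. It errs towards inclusion, so it cannot hide a stop. The visible protocol text describes lowering the AG019 dose and stopping it, but no temporary AG019 pause for an adverse event, so the affected case may never arise. SAP 7.1 also plans a subject discontinuation table and an AG019 compliance table, and a patient who resumed and finished would show high compliance there.

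Most of this is fair: there is no ambiguity, no events are lost, and the frequency is unknown. It does not remove the mismatch between title and content. The compliance table does not link events to stops, and the subject discontinuation table may concern leaving the study.

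**On relatedness.** Protocol 10.7 does not ask for tables by system organ class and preferred term. SAP 6.3.8 includes related events in the overall summary, and SAP 7.1 plans a "Summary of All Adverse Events for combination cohort patients". If that row means either product, the protocol commitment is met and the statement in SAP 6.1 is accurate. A table titled by relationship to AG019 also misleads nobody who reads the title. All events are listed individually, and a teplizumab compliance table and a listing of events in patients with infusion withholding are planned.

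This narrows the point. It would be wrong to say that teplizumab causality is reported nowhere, and the departure from Protocol 10.7 depends on what the summary row means. But the row names no product and cannot show which events were attributed to teplizumab. SAP 6.3.8 did not restrict relatedness to AG019; only the output list does.

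**Conclusion.** Both parts hold, at minor severity. Followed as written, the SAP reports a resumed AG019 interruption as a premature discontinuation. It also provides no table by system organ class and preferred term of events by relationship to teplizumab or to either product, although teplizumab is planned for 20 of 24 combination patients.

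The primary endpoint, incidence of treatment-emergent events to 6 months, is unaffected, and the study is descriptive with no test or decision rule tied to these tables. The discontinuation rule over-counts and misses nothing. Its effect depends on at least one event-driven pause that is later resumed; the documents give no rate, and the 10% to 25% range assumes exactly one such patient in the group. The relatedness gap in the output list depends on no such assumption. Whether it also breaks the Protocol 10.7 commitment depends on the undefined related-events row.

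**What to change.** These are reporting changes only; no clinical rule is altered.

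**Discontinuation**
- Preferred: count as discontinued the *withdrawn* answers plus any *interrupted* answer with no resumption by the AG019 treatment end date. Show resumed interruptions in their own row. A resumed pause is recognised by an end date later than the interruption, so the SAP should define that end date as the last capsule taken and state which dates are compared.
- Minimum: retitle the table as interruption or discontinuation and show the two CRF answers separately. This needs no derivation.

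**Relatedness**
- For the combination cohorts, add tables by system organ class and preferred term by relationship to teplizumab and to either product.
- State in SAP 6.3.8 which product the related-events row of the overall summary refers to, preferably with one row each for AG019, teplizumab and either.
- If the tables are not added, declare the narrowing in SAP 6.1.

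**Cost and timing.** SAP wording and a few extra tables. The CRF answers and both causality ratings are already collected. SAP 6.9 places decisions on blinded subjects' data before unblinding for the third interim analysis, so these definitions should be settled by then.
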